3.4 Hematologic

The following AE term, if considered Grade ≥ 3 or requiring dose modification or use of systemic steroids to treat the AE, are considered an ECI and should be reported to the Sponsor within 24 hours of the event:

Autoimmune hemolytic anemia

Aplastic anemia

Disseminated Intravascular Coagulation (DIC)

Haemolytic Uraemic Syndrome (HUS)

Idiopathic (or immune) Thrombocytopenia Purpura (ITP)

Thrombotic Thrombocytopenic Purpura (TTP)

Any Grade 4 anemia regardless of underlying mechanism

All attempts should be made to rule out other causes such as metastases, sepsis and/or infection. Relevant diagnostic studies such as peripheral blood smear, reticulocyte count, LDH, haptoglobin, bone marrow biopsy or Coomb's test, etc., should be considered to confirm the diagnosis. However the AE should be reported regardless of etiology.

Course of Action

Grade 2 events:

Report as ECI

Hold pembrolizumab

Prednisone 1-2 mg/kg daily may be indicated

Consider Hematology consultation.

Permanently discontinue for inability to reduce corticosteroid dose to 10 mg or less of prednisone or equivalent per day within 12 weeks.

Grade 3 events:

Report as ECI

Hematology consultation.

Hold pembrolizumab Discontinuation should be considered as per specific protocol guidance.

Treat with methylprednisolone 125 mg iv or prednisone 1-2 mg/kg p.o. (or equivalent) as appropriate

Permanently discontinue for inability to reduce corticosteroid dose to 10 mg or less of prednisone or equivalent per day within 12 weeks.

Grade 4 events:

Report as ECI

Hematology consultation

Discontinue pembrolizumab for all solid tumor indications; refer to protocol for hematologic malignancies.

Treat with methylprednisolone 125 mg iv or prednisone 1-2 mg/kg p.o. (or equivalent) as appropriate

3.5 Hepatic

The following AE terms, if considered \geq Grade 2 or greater (or any grade with dose modification or use of systemic steroids to treat the AE), are considered ECIs and should be reported to the Sponsor within 24 hours of the event:

Autoimmune hepatitis

Hepatitis

Transaminase elevations

All attempts should be made to rule out other causes such as metastatic disease, infection or other hepatic diseases. However the AE should be reported regardless of etiology.

Drug Induced Liver Injury (DILI)

In addition, the event must be reported as a Drug Induced Liver Injury (DILI) ECI, if the patient meets the laboratory criteria for potential DILI defined as:

An elevated alanine transaminase (ALT) or aspartate transaminase (AST) lab value that is greater than or equal to three times (3X) the upper limit of normal (ULN) and

An elevated total bilirubin lab value that is greater than or equal to two times (2X) ULN and

At the same time, an alkaline phosphatase (ALP) lab value that is less than 2X ULN,

As a result of within-protocol-specific testing or unscheduled testing.

Note that any hepatic immune ECI meeting DILI criteria should only be reported once as a DILI event.

Course of Action

Grade 2 events:

Report as ECI

Hold pembrolizumab when AST or ALT >3.0 to 5.0 times ULN and/or total bilirubin >1.5 to 3.0 times ULN.

Monitor liver function tests more frequently until returned to baseline values (consider weekly).

Treat with 0.5-1 mg/kg/day methylprednisolone or oral equivalent and when LFT returns to grade 1 or baseline, taper steroids over at least 1 month, consider prophylactic antibiotics for opportunistic infections, and resume pembrolizumab per protocol

Permanently discontinue for inability to reduce corticosteroid dose to 10 mg or less of prednisone or equivalent per day within 12 weeks.

Permanently discontinue pembrolizumab for patients with liver metastasis who begin treatment with Grade 2 elevation of AST or ALT, and AST or ALT increases $\geq 50\%$ relative to baseline and lasts ≥ 1 week.

Grade 3 events:

Report as ECI

Discontinue pembrolizumab when AST or ALT >5.0 times ULN and/or total bilirubin >3.0 times ULN.

Consider appropriate consultation and liver biopsy to establish etiology of hepatic injury, if necessary

Treat with high-dose intravenous glucocorticosteroids for 24 to 48 hours. When symptoms improve to Grade 1 or less, a steroid taper with dexamethasone 4 mg every 4 hours or prednisone at 1 to 2 mg/kg should be started and continued over no less than 4 weeks.

If serum transaminase levels do not decrease 48 hours after initiation of systemic steroids, oral mycophenolate mofetil 500 mg every 12 hours may be given. Infliximab is not recommended due to its potential for hepatotoxicity.

Several courses of steroid tapering may be necessary as symptoms may worsen when the steroid dose is decreased.

Permanently discontinue for inability to reduce corticosteroid dose to 10 mg or less of prednisone or equivalent per day within 12 weeks.

Grade 4 events:

Report as ECI

Permanently discontinue pembrolizumab

Manage patient as per Grade 3 above

3.6 Neurologic

The following AE terms, regardless of grade, are considered ECIs and should be reported to the Sponsor within 24 hours of the event:

Autoimmune neuropathy

Demyelinating polyneuropathy

Guillain-Barre syndrome

Myasthenic syndrome

All attempts should be made to rule out other causes such as metastatic disease, other medications or infectious causes. However the AE should be reported regardless of etiology.

Course of Action

Grade 2 events:

Report as ECI

Moderate (Grade 2) – consider withholding pembrolizumab.

Consider treatment with prednisone 1-2 mg/kg p.o. daily as appropriate

Consider Neurology consultation. Consider biopsy for confirmation of diagnosis.

Permanently discontinue for inability to reduce corticosteroid dose to 10 mg or less of prednisone or equivalent per day within 12 weeks.

Grade 3 and 4 events:

Report as ECI

Discontinue pembrolizumab

Obtain neurology consultation. Consider biopsy for confirmation of diagnosis

Treat with systemic corticosteroids at a dose of 1 to 2 mg/kg prednisone or equivalent once per day. If condition worsens consider IVIG or other immunosuppressive therapies as per local guidelines

When symptoms improve to Grade 1 or less, steroid taper should be started and continued over no less than 4 weeks.

3.7 Ocular

The following AE terms, if considered Grade ≥ 2 or requiring dose modification or use of systemic steroids to treat the AE, is considered an ECI and should be reported to the Sponsor within 24 hours of the event:

Uveitis

Iritis

All attempts should be made to rule out other causes such as metastatic disease, infection or other ocular disease (e.g. glaucoma or cataracts). However the AE should be reported regardless of etiology.

Course of Action

Grade 2 events:

Evaluation by an ophthalmologist is strongly recommended.

Treat with topical steroids such as 1% prednisolone acetate suspension and iridocyclitics.

Discontinue pembrolizumab as per protocol if symptoms persist despite treatment with topical immunosuppressive therapy.

Grade 3 events:

Evaluation by an ophthalmologist is strongly recommended

Hold pembrolizumab and consider permanent discontinuation as per specific protocol guidance.

Treat with systemic corticosteroids such as prednisone at a dose of 1 to 2 mg/kg per day. When symptoms improve to Grade 1 or less, steroid taper should be started and continued over no less than 4 weeks.

Permanently discontinue for inability to reduce corticosteroid dose to 10 mg or less of prednisone or equivalent per day within 12 weeks.

Grade 4 events:

Evaluation by an ophthalmologist is strongly recommended

Permanently discontinue pembrolizumab.

Treat with corticosteroids as per Grade 3 above

3.8 Renal

The following AEs if \geq Grade 2 are considered ECIs and should be reported to the Sponsor within 24 hours of the event:

Nephritis

Nephritis autoimmune

Renal failure

Renal failure acute

Creatinine elevations \geq Grade 3 or any grade with dose modification or use of systemic steroids to treat the AE.

All attempts should be made to rule out other causes such as obstructive uropathy, progression of disease, or injury due to other chemotherapy agents. A renal consultation is recommended. However the AE should be reported regardless of etiology.

Course of Action

Grade 2 events:

Hold pembrolizumab

Treatment with prednisone 1-2 mg/kg p.o. daily.

Permanently discontinue for inability to reduce corticosteroid dose to 10 mg or less of prednisone or equivalent per day within 12 weeks.

Grade 3-4 events:

Discontinue pembrolizumab

Renal consultation with consideration of ultrasound and/or biopsy as appropriate

Treat with systemic corticosteroids at a dose of 1 to 2 mg/kg prednisone IV or equivalent once per day.

When symptoms improve to Grade 1 or less, steroid taper should be started and continued over no less than 4 weeks.

3.9 Skin

Rash and Pruritus

The following AEs should be considered as ECIs, if \geq Grade 3 and should be reported to the Sponsor within 24 hours of the event:

Pruritus

Rash

Rash generalized

Rash maculo-papular

In addition to CTCAE Grade 3 rash, any rash that is considered clinically significant, in the physician's judgment, should be treated as an ECI. Clinical significance is left to the physician to determine, and could possibly include rashes such as the following:

rash with a duration >2 weeks; OR

rash that is >10% body surface area; OR

rash that causes significant discomfort not relieved by topical medication or temporary cessation of study drug.

Other Skin ECIs

The following AEs should always be reported as ECIs, regardless of grade, and should be reported to the Sponsor within 24 hours of the event:

Dermatitis exfoliative

Erythema multiforme

Steven's Johnson syndrome

Toxic epidermal necrolysis

Please note, the AE should be reported regardless of etiology.

Course of Action

Grade 2 events:

Symptomatic treatment should be given such as topical glucocorticosteroids (e.g., betamethasone 0.1% cream or hydrocortisone 1%) or urea-containing creams in combination with oral anti-pruritics (e.g., diphenhydramine HCl or hydroxyzine HCl).

Treatment with oral steroids is at physician's discretion for Grade 2 events.

Grade 3 events:

Hold pembrolizumab.

Consider Dermatology Consultation and biopsy for confirmation of diagnosis.

Treatment with oral steroids is recommended, starting with 1 mg/kg prednisone or equivalent once per day or dexamethasone 4 mg four times orally daily. When symptoms improve to Grade 1 or less, steroid taper should be started and continued over no less than 4 weeks.

Permanently discontinue for inability to reduce corticosteroid dose to 10 mg or less of prednisone or equivalent per day within 12 weeks.

Grade 4 events:

Permanently discontinue pembrolizumab.

Dermatology consultation and consideration of biopsy and clinical dermatology photograph.

Initiate steroids at 1 to 2 mg/kg prednisone or equivalent. When symptoms improve to Grade 1 or less, steroid taper should be started and continued over no less than 4 weeks.

3.9.1. Immediate Evaluation for Potential Skin ECIs

A. Photographs:

Every attempt should be made to get a photograph of the actual ECI skin lesion or rash as soon as possible. Obtain appropriate consent for subject photographs if a consent form addendum is required by your IRB/ERC.

Take digital photographs of:

the head (to assess mucosal or eye involvement),

the trunk and extremities, and

a close-up of the skin lesion/rash.

If possible, a ruler should be placed alongside the site of a skin occurrence as a fixed marker of distance.

The time/date stamp should be set in the 'ON' position for documentation purposes.

Photographs should be stored with the subject's study records.

The Sponsor may request copies of photographs. The local study contact (e.g., CRA) will provide guidance to the site, if needed.

B. Past Medical History:

Collect past medical history relevant to the event, using the questions in Appendix 2 (Past Medical History Related to Dermatologic Event) as a guide. Any preexisting conditions not previously reported (e.g., drug allergy) should be entered into the Medical History eCRF.

C. Presentation of the Event:

Collect information on clinical presentation and potential contributing factors using the questions in Appendix 3 (Presentation of the Dermatologic Event) as a guide. This information should be summarized and entered in narrative format in the AE eCRF. Please use the available free-text fields, such as Signs and Symptoms. Note pertinent negatives where applicable to reflect that the information was collected. Any treatments administered should be entered on the Concomitant Medication eCRF.

D. Vitals Signs and Standard Laboratory Tests:

Measure vital signs (pulse, sitting BP, oral temperature, and respiratory rate) and record on the Vital Signs eCRF. Perform standard laboratory tests (CBC with manual differential and serum chemistry panel, including LFTs).

E. Focused Skin Examination:

Perform a focused skin examination using the questions in Appendix 4 (Focused Skin Examination) as a guide. Information should be summarized and entered on the Adverse Experience eCRF as part of the narrative.

F. Dermatology Consult

Refer the subject to a dermatologist as soon as possible.

For a “severe rash”, the subject must be seen within 1-2 days of reporting the event.

For clinically significant rash, the subject should be seen within 3-5 days.

The dermatologist should submit a biopsy sample to a certified dermatopathology laboratory or to a pathologist experienced in reviewing skin specimens.

The site should provide the dermatologist with all relevant case history, including copies of clinical photographs and laboratory test results.

3.10 Other

The following AEs, regardless of grade, are considered ECIs and should be reported to the Sponsor within 24 hours of the event:

Myocarditis

Pericarditis

Pancreatitis

Any additional Grade 3 or higher event which the physician considers to be immune related

All attempts should be made to rule out other causes. Therapeutic specialists should be consulted as appropriate. However the AE should be reported regardless of etiology.

Course of Action

Grade 2 events or Grade 1 events that do not improve with symptomatic treatment:

Withhold pembrolizumab.

Systemic corticosteroids may be indicated.

Consider biopsy for confirmation of diagnosis.

If pembrolizumab held and corticosteroid required, manage as per grade 3 below.

Grade 3 events:

Hold pembrolizumab

Treat with systemic corticosteroids at a dose of 1 to 2 mg/kg prednisone or equivalent once per day.

When symptoms improve to Grade 1 or less, steroid taper should be started and continued over no less than 4 weeks.

Permanently discontinue for inability to reduce corticosteroid dose to 10 mg or less of prednisone or equivalent per day within 12 weeks. Otherwise, pembrolizumab treatment may be restarted and the dose modified as specified in the protocol

Grade 4 events:

Treat with systemic corticosteroids at a dose of 1 to 2 mg/kg prednisone or equivalent once per day.

Discontinue pembrolizumab

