5.6 Subject Withdrawal/Discontinuation Criteria

Subjects may withdraw consent at any time for any reason or discontinue treatment.

In this trial, a subject may discontinue from study treatment for the reason outlined below but will remain in the trial for follow up as outlined in Section 6.7, as long as the subject does not withdraw consent. Discontinuation from study treatment is permanent. Once a subject has discontinued study treatment for the reason outlined below, he/she shall not be allowed to begin study treatment again (This is distinct and different from infusion / treatment delays required due to adverse events. For guidelines for management of toxicity and schedule modification and supportive care guidelines please refer to [Appendix G](#) and [Appendix H](#)). A subject should stop the study treatment (but should be encouraged to continue to be monitored/followed-up in the trial) for any of the following reasons:

- ◆ The subject or legal representative (such as legal guardian) withdraws consent;
- ◆ Disease recurrence by RECIST version 1.1;

- ◆ Unacceptable adverse events;
- ◆ The subject's treatment assignment has been unblinded by the investigator, MSD subsidiary, or through the emergency unblinding call center.
- ◆ Any progression or recurrence of any malignancy, or any occurrence of another malignancy that require active treatment;
- ◆ Inter-current illness (including second malignancy) that, in the opinion of the investigator, warrants the patient's withdrawal from study treatment;
- ◆ Any study intervention-related toxicity specified as a reason for permanent discontinuation as defined in the guidelines for dose modification due to AE in [Appendix G](#) and [Appendix H](#).
- ◆ Investigator's decision to withdraw the subject;
- ◆ The participant has a medical condition or personal circumstance which, in the opinion of the investigator and/or Sponsor, placed the participant at unnecessary risk from continued administration of study intervention.
- ◆ The subject has a positive pregnancy test or is pregnant;
- ◆ Noncompliance with trial study treatment or procedure requirements;
- ◆ Administrative reasons.

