5.7 Management of toxicity

For management of toxicity and supportive care guidelines please refer to [Appendix G](#) and [Appendix H](#).

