7.2.3 Serious adverse events

Serious adverse events are defined by the Good Clinical Practice Guideline.

**SERIOUS ADVERSE EVENTS SHOULD BE IMMEDIATELY REPORTED
ACCORDING TO THE PROCEDURE DETAILED IN THIS PROTOCOL** (see
Chapter on Reporting Serious Adverse Events)

**For guidance regarding Events of Clinical Interest (ECI) for pembrolizumab please
refer to [Appendix I](#).**

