Hypophysitis	Grade 2	Withhold	
 • Administer corticosteroids and initiate hormonal replacements as clinically indicated 	
 • Monitor for signs and symptoms of hypophysitis (including hypopituitarism and adrenal insufficiency)
	Grade 3 or 4	Withhold or permanently discontinue ^d		
Hyperthyroidism	Grade 2	Continue	
 • Treat with non-selective beta-blockers (eg, propranolol) or thionamides as appropriate 	
 • Monitor for signs and symptoms of thyroid disorders
	Grade 3 or 4	Withhold or permanently discontinue ^d		

General instructions:
 
 Severe and life-threatening irAEs should be treated with IV corticosteroids followed by oral steroids. Other immunosuppressive treatment should begin if the irAEs are not controlled by corticosteroids. Pembrolizumab must be permanently discontinued if the irAE does not resolve or the corticosteroid dose is not ≤ 10 mg/day within 12 weeks of the last pembrolizumab treatment. The corticosteroid taper should begin when the irAE is \leq Grade 1 and continue at least 4 weeks. If pembrolizumab has been withheld, pembrolizumab may resume after the irAE decreased to \leq Grade 1 after corticosteroid taper. 				
Hypothyroidism	Grade 2, 3, 4	Continue	
 Initiate thyroid replacement hormones (eg, levothyroxine or liothyronine) per standard of care 	
 Monitor for signs and symptoms of thyroid disorders
Nephritis: grading according to increased creatinine or acute kidney injury	Grade 2	Withhold	
 Administer corticosteroids (prednisone 1 – 2 mg/kg or equivalent) followed by taper 	
 Monitor changes of renal function
	Grade 3 or 4	Permanently discontinue		
Myocarditis	Grade 1 or 2	Withhold	
 Based on severity of AE administer corticosteroids 	
 Ensure adequate evaluation to confirm etiology and/or exclude other causes
	Grade 3 or 4	Permanently discontinue		
All Other immune-related AEs	Persistent Grade 2	Withhold	
 Based on severity of AE administer corticosteroids 	
 Ensure adequate evaluation to confirm etiology or exclude other causes
	Grade 3	Withhold or discontinue based on the event ^e		

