	Recurrent Grade 3 or Grade 4	Permanently discontinue		

^a AST/ALT: $>3.0 - 5.0 \times$ ULN if baseline normal; $>3.0 - 5.0 \times$ baseline, if baseline abnormal; bilirubin: $>1.5 - 3.0 \times$ ULN if baseline normal; $>1.5 - 3.0 \times$ baseline if baseline abnormal
 
^b AST/ALT: >5.0 to $20.0 \times$ ULN, if baseline normal; $>5.0 - 20.0 \times$ baseline, if baseline abnormal; bilirubin: $>3.0 - 10.0 \times$ ULN if baseline normal; $>3.0 - 10.0 \times$ baseline if baseline abnormal
 
^c AST/ALT: $>20.0 \times$ ULN, if baseline normal; $>20.0 \times$ baseline, if baseline abnormal; bilirubin: $>10.0 \times$ ULN if baseline normal; $>10.0 \times$ baseline if baseline abnormal
 
^d The decision to withhold or permanently discontinue pembrolizumab is at the discretion of the investigator or treating physician. If control achieved or \leq Grade 2, pembrolizumab may be resumed.
 
^e Events that require discontinuation include but are not limited to: Guillain-Barre Syndrome, encephalitis, Stevens-Johnson Syndrome and toxic epidermal necrolysis.
				

Patients who have a Grade 2 endocrinopathy, requiring ongoing hormonal replacement therapy, may restart pembrolizumab if treatment interruption was less than 12 weeks.

Dosing interruptions are permitted in the case of medical / surgical events or logistical reasons not related to study therapy (e.g., elective surgery, unrelated medical events, patient vacation, and/or holidays). Subjects should be placed back on study therapy within 3 weeks of the scheduled interruption, but no more than a maximum of 12 weeks for each instance. If the interruption is greater than 12 weeks the PI must discuss continuation in the trial with the Sponsor prior to administering additional therapy. For more info, please refer to Section [6.3](#).

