Appendix H: Supportive care

Subjects should receive appropriate supportive care measures as deemed necessary by the treating investigator. Suggested supportive care measures for the management of adverse events with potential immunologic etiology are outlined below and in greater detail in the ECI guidance document. Where appropriate, these guidelines include the use of oral or intravenous treatment with corticosteroids as well as additional anti-inflammatory agents if symptoms do not improve with administration of corticosteroids. Note that several courses of steroid tapering may be necessary as symptoms may worsen when the steroid dose is decreased. For each disorder, attempts should be made to rule out other causes such as metastatic disease or bacterial or viral infection, which might require additional supportive care. The treatment guidelines are intended to be applied when the investigator determines the events to be related to pembrolizumab.

Note: if after the evaluation the event is determined not to be related, the investigator is instructed to follow the ECI reporting guidance but does not need to follow the treatment guidance (as outlined in the ECI guidance document). Refer to Section 5.2.1 for infusion modification.

It may be necessary to perform conditional procedures such as bronchoscopy, endoscopy, or skin photography as part of evaluation of the event. Suggested conditional procedures, as appropriate, can be found in the ECI guidance document.

◆ **Pneumonitis:**

- ◆ For **Grade 2 events**, treat with systemic corticosteroids. When symptoms improve to Grade 1 or less, steroid taper should be started and continued over no less than 4 weeks.
- ◆ For **Grade 3-4 events**, immediately treat with intravenous steroids. Administer additional anti-inflammatory measures, as needed.
- ◆ Add prophylactic antibiotics for opportunistic infections in the case of prolonged steroid administration.

◆ **Diarrhea/Colitis:**

Subjects should be carefully monitored for signs and symptoms of enterocolitis (such as diarrhea, abdominal pain, blood or mucus in stool, with or without fever) and of bowel perforation (such as peritoneal signs and ileus).

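### For Grade 3 myocarditis, Appendix I section 3.10 says hold and permits restart, while Appendix G requires permanent discontinuation

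*Combined protocol and SAP*

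**What the plan says.** **Appendix G, Table 1.** Myocarditis has its own row. Grade 1 or 2 is withheld. At Grade 3 or 4 the action is to "permanently discontinue". Footnote d, which leaves the choice to the investigator, is attached to the diabetes, hypophysitis and hyperthyroidism rows but not to this one. Footnote e, attached to Grade 3 events in the row for all other immune-related events, reads: "Events that require discontinuation include but are not limited to: Guillain-Barre Syndrome, encephalitis, Stevens-Johnson Syndrome and toxic epidermal necrolysis".

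**Appendix I, section 3.10 (Other).** Myocarditis is the first event listed, at any grade. At Grade 3 the instruction is to hold, give systemic steroids, and stop permanently only if the steroid dose cannot be reduced to 10 mg a day or less within 12 weeks. The next sentence is "Otherwise, pembrolizumab treatment may be restarted and the dose modified as specified in the protocol". Grade 4 is a discontinuation. The Overview of Appendix I defines a hold as a stop after which resumption may be considered for a patient who meets the resumption criteria.

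**Protocol body.** Section 5.6 lists among the reasons to stop treatment "Any study intervention-related toxicity specified as a reason for permanent discontinuation as defined in the guidelines for dose modification due to AE in" Appendices G and H, and says that after a discontinuation "he/she shall not be allowed to begin study treatment again". Section 5.7 reads "For management of toxicity and supportive care guidelines please refer to" Appendices G and H; it does not mention Appendix I. Section 7.2.3, on serious adverse events, opens its pointer to Appendix I with "For guidance regarding Events of Clinical Interest (ECI) for pembrolizumab please".

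**The concern.** The same event at the same grade has two different default actions within one protocol: an unconditional permanent stop in one appendix, a conditional hold with restart in another. Section 3.10 contains no carve-out for myocarditis, and no sentence says expressly that Appendix G prevails over Appendix I.

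A site managing a case has a reason to open 3.10. The Appendix G row says only that steroids depend on severity, and Appendix H has no myocarditis entry. The one steroid dose given for it (1 to 2 mg/kg prednisone or equivalent daily) is in 3.10, a few lines above the restart sentence. A site working from 3.10 alone could rechallenge a patient whom Appendix G requires to stop. That would be a safety exposure in patients with no evidence of disease at entry, and a deviation from Section 5.6.

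**Working it through.** No arithmetic beyond counting applies. The check sets the Grade 3 instructions side by side and then looks for text that reconciles them.

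**Step 1. Named Appendix G rows that make a first Grade 3 event an unconditional permanent stop.**

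| Event | Appendix G, Grade 3 | Appendix I, Grade 3 | Result |
|---|---|---|---|
| Pneumonitis | permanent stop | discontinue (3.1) | match |
| AST, ALT or bilirubin | permanent stop | discontinue (3.5) | match |
| Nephritis | permanent stop | discontinue (3.8) | match |
| Myocarditis | permanent stop | hold, may restart (3.10) | conflict |

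Count: 3 of 4 match, 1 of 4 conflicts.

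**Step 2. The four footnote e events, taken at Grade 3.**

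| Event | Appendix I, Grade 3 | Result |
|---|---|---|
| Guillain-Barre syndrome | discontinue (3.6) | match |
| Stevens-Johnson syndrome | hold (3.9) | differs |
| Toxic epidermal necrolysis | hold (3.9) | differs |
| Encephalitis | not named; an immune-related case falls under the 3.10 catch-all, hold and may restart | differs |

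Count: 1 of 4 matches, 3 of 4 differ. The skin entries differ less sharply than myocarditis: 3.9 has no restart sentence, so restart is implied only by the definition of a hold.

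**Step 3. Myocarditis at each grade.**

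- Grade 1: Appendix G withholds; 3.10 withholds only if the event does not improve with symptomatic treatment.
- Grade 2: both withhold.
- Grade 3: permanent stop against hold with conditional restart.
- Grade 4: both discontinue.

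The contradiction over stopping for good is therefore confined to Grade 3. The other two events named in 3.10, pericarditis and pancreatitis, fall in Appendix G's row for all other events, where Grade 3 may be withheld or discontinued according to the event; that is compatible with 3.10.

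**Step 4. Text that reconciles the two.** Section 5.6 makes the permanent stops in Appendices G and H binding and final. Section 5.7 names only those two appendices. The Overview of Appendix I calls its recommendations guidelines and tells sites to follow the protocol's wording on dose modification. All of this points to Appendix G.

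**Step 5. Text that pulls the other way.** The same Overview says that its guidance gives specific direction on when to hold or discontinue for each immune-related event. Appendix H says that supportive measures are set out in more detail in the ECI guidance document, and that for an event judged unrelated the investigator "does not need to follow the treatment guidance (as outlined in the ECI guidance document"), which implies that for a related event the guidance is to be followed. The resumption check may also fail to catch the error: the general instructions in Appendix G allow resumption once a withheld event is Grade 1 or less after taper, and a patient already held under 3.10 could meet that unless the site rereads the myocarditis row.

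**Step 6. Where Appendix I is the stricter document.** At Grade 4 hyperthyroidism, Appendix I (3.3) discontinues, while Appendix G allows either withholding or discontinuation. For Grade 3 events listed in 3.6 (neurologic), Appendix I discontinues, while Appendix G's row for other events leaves it to the event. This limits how a precedence sentence can be worded.

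**The case against.** The strongest reply is that precedence is already supplied. Appendix I is a programme-wide document, so the protocol to which it defers is this trial's protocol, and Section 5.6 places the stopping rule in Appendices G and H. The restart sentence itself refers back to the protocol. A reader might infer that the trial permits rechallenge after Grade 3 myocarditis, or that the governing rule is undetermined. The documents support neither: read together, they lead to a permanent stop. That stands, and it limits the practical risk. It does not remove the contrary wording from the page that a site would consult.

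There is a further safeguard. Sections 16.1 and 16.6 require myocarditis of any grade to be reported within 24 hours. Under 3.10 a steroid taper, begun once the event is Grade 1 or less, runs for at least 4 weeks, so the safety team should know of the case well before any restart. This also stands.

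The pointers to Appendix I are not dosing instructions. Section 7.2.3 concerns serious adverse events, and the Appendix H text concerns supportive care and events judged unrelated. That is fair; they show why sites would open Appendix I, not that it governs dosing.

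The counts can also be questioned. They cover first Grade 3 events only. Appendix G's permanent stops for recurrent Grade 3 colitis and recurrent Grade 3 other events are left out. The footnote e count assumes that each event can be graded 3, which cannot be checked because the CTCAE is linked rather than reproduced. The myocarditis conflict does not depend on either count.

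Finally, the benefit depends on timing. Accrual of 52 months from January 2016 ends in about spring 2020, and about one year of treatment takes dosing to about spring 2021, later with delays. If dosing is over, the change protects no current patient. The text reviewed does not show its own date.

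**Conclusion.** The inconsistency is real and should be fixed. It rests on two explicit instructions for the same event and grade, with no discretion footnote on one side and no exception on the other. It is one conflicting cell among four comparable rows, plus three weaker differences under footnote e.

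A reader might infer that Appendix I is broadly out of line with Appendix G. It is not: it matches the pneumonitis, hepatic and renal stops. Nor do the documents give any basis for estimating how many patients could be affected, and none is claimed. The conclusion that Appendix G governs is an inference from Sections 5.6 and 5.7 and Appendix I's deference clause, since no sentence ranks the two appendices. No endpoint, power, alpha or analysis is affected.

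**What to change.** 1. In Appendix I, section 3.10, state that myocarditis follows Appendix G: withhold at Grade 1 or 2, permanently discontinue at Grade 3 or 4.
2. In Section 5.7, add one sentence: any permanent discontinuation required by Appendix G applies even where Appendix I says hold, and stricter stops in Appendix I are not relaxed. This also settles Stevens-Johnson syndrome, toxic epidermal necrolysis and encephalitis under footnote e.
3. Notify sites.

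A blanket statement that Appendix G governs wherever the two differ should be avoided, because it would loosen the Appendix I stops for Grade 4 hyperthyroidism and Grade 3 neurologic events. If the sponsor prefers not to edit a version-controlled programme document, the sentence in Section 5.7 resolves the stopping rule by itself, but leaves the misleading text in 3.10.

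The cost is a small wording change carried in a protocol amendment, with the regulatory and ethics review that Appendix J requires, and a notice to sites. Design, sample size and analysis do not change.
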